2.2 SAFETY OBJECTIVE

The safety objective for this study is to evaluate the safety of MSTT1041A compared with placebo on the basis of the following endpoints:

- Incidence and severity of adverse events, with severity determined according to the WHO toxicity scale
- Change from randomization visit in vital signs, ECGs, and clinical laboratory results

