- Patient is not eligible, if HBV DNA test value is ≥ 20 IU/mL or test cannot be performed.
- Patient is eligible, if HBV DNA test value is < 20 IU/mL.
- Evidence of active liver disease, including jaundice or AST, ALT, total bilirubin, or ALP $> 2 \times$ upper limit of normal (ULN) at screening

- History of anaphylaxis, hypersensitivity to a biologic agent, or known hypersensitivity to any component of the MSTT1041A or placebo injection
- Neutrophil count $\leq 0.5 \times 10^3/\mu\text{L}$ at screening
- Platelet count $\leq 50 \times 10^3/\mu\text{L}$ at screening
- Presence of skin comorbidities that may interfere with study assessments, in the opinion of the investigator
- Active malignancy, including cutaneous basal or squamous cell carcinoma or melanoma
- History of malignancy within 5 years before screening, except for cases of cervical carcinoma in situ or breast ductal carcinoma in situ that have been treated and considered cured
- Helminthic parasitic infection diagnosed within 6 months before screening that has not been treated or has not responded to standard-of-care therapy or exposure to water-born parasites within 6 weeks before screening
- History or evidence of substance abuse that would pose a risk to patient safety, interfere with the conduct of the study, have an impact on the study results, or affect the patient's ability to participate in the study, in the opinion of the investigator
- Hemoglobin A1c (HbA_{1c}) $> 8.5\%$ at screening or any other clinically significant finding that, in the opinion of the investigator, may define uncontrolled diabetes
- History of myocardial infarction, congestive heart failure NYHA Class III and IV, unstable angina pectoris, or stroke within 12 months before screening
- History or presence of complete left bundle branch block, second- or third-degree atrioventricular heart block, or evidence of prior myocardial infarction on ECG, or any abnormality that is clinically significant in the investigator's opinion
- QT interval corrected through use of Fridericia's formula (QTcF) > 450 ms, if patient is male, or QTcF > 470 ms, if patient is female

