4.3.2 Study Treatment Dosage, Administration, and Compliance

The treatment regimens are summarized in Section [3.1](#).

No dose modifications should be performed in this study. Any dose modification should be noted on the Study Drug Administration electronic Case Report Form (eCRF). Cases of accidental overdose or medication error, along with any associated adverse events, should be reported as described in Section [5.4.4](#).

Guidelines for treatment interruption or discontinuation for patients who experience adverse events are provided in Section [5.1.2.1](#).

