4.5.7 Electrocardiograms

Single ECG recordings will be obtained at specified timepoints, as outlined in the schedule of activities (see [Appendix 1](#)), and may be obtained at unscheduled timepoints as indicated.

All ECG recordings must be performed using a standard high-quality, high-fidelity digital electrocardiograph machine equipped with computer-based interval measurements. Lead placement should be as consistent as possible. ECG recordings must be performed after the patient has been resting in a supine position for at least 10 minutes. All ECGs are to be obtained prior to other procedures scheduled at that same time (e.g., blood draws). Circumstances that may induce changes in heart rate, including environmental distractions (e.g., television, radio, conversation) should be avoided during the pre-ECG resting period and during ECG recording.

For safety monitoring purposes, the investigator must review, sign, and date all ECG tracings. Paper copies of ECG tracings will be kept as part of the patient's permanent study file at the site. Digital recordings will be stored at central ECG laboratory, and the data will be sent to the Sponsor, using the Sponsor's standard procedures to handle and process the electronic transfer of these data. Any clinically significant morphologic waveform changes or other ECG abnormalities must be documented on the appropriate eCRF. If considered appropriate by the Sponsor, ECGs may be analyzed retrospectively at a central laboratory.

If at a particular postdose timepoint the mean QTcF is > 500 ms and/or > 60 ms longer than the baseline value, another ECG must be recorded, ideally within the next 5 minutes, and ECG monitoring should continue until QTcF has stabilized on two successive ECGs. The same procedure should be repeated approximately 30 minutes after QTcF has stabilized on two successive ECGs of the first measurement. The Medical Monitor should be notified. Standard-of-care treatment may be instituted per the discretion of the investigator. If a PK sample is not scheduled for that timepoint, an unscheduled PK sample should be obtained. A decision on study drug discontinuation should be made, as described in Section [5.1.2.3](#). The investigator should also evaluate the patient for potential concurrent risk factors (e.g., electrolyte abnormalities, co-medications known to prolong the QT interval, severe bradycardia).

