5.1.2.3 Management of Increases in QT Interval

Study drug should be discontinued in patients who develop any of the following, unless there is a clear alternative cause for the changes:

- Sustained (at least two ECG measurements >30 minutes apart) QTcF that is >500 ms and >60 ms longer than the baseline value
- Sustained absolute QTcF that is >515 ms
- An episode of torsades de pointes or a new ECG finding of clinical concern

Of note, if there is a new intraventricular conduction block, the increase in QRS complex duration should be subtracted from the QTcF change, because this represents an increase in QTcF unrelated to alterations in repolarization. Also of note, it is not uncommon to record arrhythmias such as non-sustained ventricular tachycardia, supraventricular tachycardia, pauses, or atrial fibrillation in healthy volunteers receiving placebo during periods of extended ECG monitoring. Therefore, it is critical that expert cardiology advice be sought to confirm any ECG changes and to ascertain the likelihood of a drug-induced arrhythmia versus the background occurrence of this arrhythmia. In such a situation, saving all available ECG data is highly suggested.

Management of patients with sustained QTcF prolongation should include close monitoring, with ECGs repeated at least hourly until two successive ECGs show resolution of the findings, correction of any electrolyte abnormalities, and possible discontinuation of other concomitant medications that are known to prolong the QT interval. Consultation with a cardiologist or electrophysiologist is recommended to help in the management of such patients.

In rare circumstances, it may be acceptable to resume study drug at a lower dose, provided that any ECG abnormalities have resolved and the patient is appropriately monitored. Clinical judgment should be applied.

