6.5 SAFETY ANALYSES

The safety analysis population will consist of all randomized patients who received at least one dose of study drug, with patients grouped according to actual treatment received.

Safety will be assessed by adverse events, clinical laboratory evaluations, vital signs, and ECGs. All verbatim adverse event terms will be mapped to MedDRA thesaurus terms, and adverse event severity will be graded according to the WHO toxicity grading. The incidence of mapped adverse events will be summarized by treatment arm.

A treatment emergent adverse event is defined as any new adverse event reported or any worsening of an existing condition on or after the first dose of study drug. Treatment emergent adverse event will be summarized by treatment arm. Clinical laboratory data (hematology and serum chemistry), vital signs, and ECGs will be summarized by descriptive statistics by treatment groups at each visit. In addition, separate summaries will be generated for serious adverse events, adverse events of special interest, deaths, pregnancies, malignancies, adverse events leading to discontinuation from the study, and adverse events leading to discontinuation of study drug.

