
Appendix 1: Schedule of Activities

	SCR	Treatment Period												FU	EOS	
		V1	V2	V3	V4	V5	V6	V7	V8	V9	V10	V11	V12			
Visit																
Week	D –35 to –1	D1	W1	W2	W4	W6	W8	W10	W12	W14	W16	W20	W24			
			D8	D15	D29	D43	D57	D71	D85	D99	D113	D141	D169			
(Visit window in days)			(± 2)	(± 3)	(± 4)	(± 4)	(± 4)	(± 4)	(± 4)	(± 4)	(± 4)	(± 4)	(± 5)	(± 5)	ET ^a	UV ^b
Office/Phone visit	O	O	O	O or P	O	P	O	P	O	P	O	P	O	O	O	O
Vital signs ⁱ	x	x	x		x		x		x		x		x	x	x	
ECG (12-lead, single)	x						x				x		x	x	x	
Serum pregnancy test ^j	x															x
Urine pregnancy test ^j		x	x		x		x		x		x		x	x	x	
Hepatitis B/C serology	x															
Hepatitis B DNA	x										x			x		
TB test	x															
Chest X-ray, TB worksheet ^k	x															
Hematology ^l	x	x	x		x		x		x		x		x	x	x	
Chemistry ^m	x	x			x		x		x		x		x	x	x	
NT-proBNP		x													x ⁿ	
Urinalysis ^o	x	x									x			x		
HbA ₁ C	x										x		x	x	x	
Fasted glucose and lipids ^p		x									x		x	x	x	
Serum PK ^q		x	x		x		x		x		x		x	x	x	
Serum specific IgE		x														

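### As Appendix 1 reads, the ECG endpoint refers to a visit with no scheduled ECG; separately, 5.1.2.3 allows an unspecified lower dose although 4.3.2 rules out dose modification

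*Combined protocol and SAP*

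**What the plan says.** **ECG reference**

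- The synopsis and Section 2.2 give the same safety endpoint: "Change from randomization visit in vital signs, ECGs, and clinical laboratory results". The protocol equates the randomization visit with Day 1.
- Section 4.5.7 leaves ECG timing to Appendix 1. The Appendix 1 row that begins "ECG (12-lead, single" shows one mark before dosing, in the screening column, and none on Day 1.
- Section 4.5.7 requires a further recording when mean QTcF exceeds 500 ms and/or is more than 60 "ms longer than the baseline value, another ECG must be recorded, ideally within the next 5 minutes".
- Section 5.1.2.3 lists among its stopping criteria "Sustained (at least two ECG measurements >30 minutes apart) QTcF that is >500 ms and >60 ms longer than the baseline value", and also "Sustained absolute QTcF that is >515 ms".
- Section 6.5 says that "vital signs, and ECGs will be summarized by descriptive statistics by treatment groups at each visit". It names no ECG baseline.

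**Dose after a QT event**

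- Section 4.3.2: "No dose modifications should be performed in this study". It adds that any modification is to be recorded on the eCRF.
- Section 4.3.2.1 lets a patient who stopped for intolerance resume once the event has resolved, if the investigator judges it unrelated to study drug and the Medical Monitor agrees.
- Section 5.1.2.3 calls for discontinuation after a QT stopping event unless there is a clear alternative cause. Its last paragraph then allows, in rare cases, resumption at a lower dose once the ECG has normalized and with suitable monitoring. No dose is given.

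**The concern.** An endpoint defined as change from a named visit needs a measurement at that visit. If no ECG is scheduled on Day 1, a programmer following Section 2.2 literally has nothing to subtract, and one following common practice uses the screening ECG without authority from the text. The same gap reaches the two QTcF rules, because both measure an increase from a baseline whose visit is not stated. Usage elsewhere does not settle it: Section 4.5.4 treats findings at the screening examination as baseline, while Table 1 in Section 5.1.2.2 refers laboratory recovery to the randomization visit.

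The dosing point is a conflict between instructions to sites. It concerns patients who have just met a cardiac stopping rule, in a trial where Section 5.1.1.5 names ECG assessment among the tools for monitoring a potential cardiovascular risk. The lower-dose option carries neither the relatedness condition nor the Medical Monitor agreement that Section 4.3.2.1 requires.

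**Working it through.** No sample size, power or alpha figure enters this point. The check compares sections and reads one table.

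**1. Which visits have an ECG?** Appendix 1 has 15 visit columns: screening, Day 1, Weeks 1, 2, 4, 6, 8, 10, 12, 14, 16, 20 and 24, early termination (ET) and unscheduled (UV). Assigning the cells of each row to these columns gives:

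| Row | Marks |
|---|---|
| ECG | Screening, W8, W16, W24, ET, UV |
| Vital signs | Screening, Day 1, W1, W4, W8, W12, W16, W24, ET, UV |
| Hematology | Screening, Day 1, W1, W4, W8, W12, W16, W24, ET, UV |
| Chemistry | Screening, Day 1, W4, W8, W12, W16, W24, ET, UV |
| HbA1c | Screening, W16, W24, ET, UV |

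Vital signs, hematology and chemistry have a Day 1 value. ECG does not, and neither does HbA1c, which is also a clinical laboratory result.

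**2. Can the table be trusted?** Only in part.

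- On the page with the ECG row, the Office/Phone line has 16 entries for 15 columns, and the line of visit windows has eight ±4-day cells where the first page of the appendix has seven.
- On the following page the randomization mark falls under Week 1. The ADA row has a Week 1 mark and no Day 1 mark, although Section 4.2 provides for baseline ADA samples.
- In favor of the reading, every ECG mark falls on screening, an office visit, ET or UV, and the neighboring rows line up sensibly.
- A screening ECG also fits Section 4.1.2, which excludes patients with QTcF above "450 ms, if patient is male, or QTcF > 470 ms, if patient is female", although that criterion names no visit.

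These checks would reveal a shifted row. They would not reveal a single lost mark.

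**3. How old can the reference be?** Screening runs from Day -35 to Day -1, followed by Day 1 with no Day 0. Day -35 to Day -1 is 34 days, and Day -1 to Day 1 is one more: 34 + 1 = 35 days at most.

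**4. Is baseline defined elsewhere for ECG?** Sections 4.5.7, 5.1.2.3 and 6.5 do not define it, and the endpoint itself names the randomization visit instead.

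**5. Dosing instructions after a QT stopping event, side by side**

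| Section | Resume? | Dose | Conditions |
|---|---|---|---|
| 4.3.2 | Not addressed | No modification | Any modification is recorded |
| 4.3.2.1 | Yes | No reduction mentioned | Event resolved, judged unrelated, Medical Monitor agrees |
| 5.1.2.1 | Interruption possible for related toxicity | No reduction mentioned | Medical Monitor discussion after two or more withheld dosing visits |
| 5.1.2.3 | Yes, rarely | Lower, level not stated | ECG resolved, patient monitored, clinical judgment |

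Only Section 5.1.2.3 contemplates a reduced dose. It neither states a level nor refers to Section 4.3.2. Because its exception for a clear alternative cause comes earlier, the lower-dose sentence can reach patients in whom no such cause was found.

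**The case against.** **The table.** The ECG point rests on one empty cell in a table whose layout is visibly damaged, while two clean prose statements name the randomization visit. That stands as a condition. A reader might infer that the ECG endpoint simply cannot be computed. The documents do not support so flat a statement: if a Day 1 mark was lost in the table, the reference exists. The undefined QTcF baseline and the dosing conflict are in prose and do not depend on the table.

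**The practical effect.** With one pre-dose ECG scheduled, everyone would use it. That stands too. A reader might also infer that the undefined baseline shifts the stopping rule. With reference R, the sustained-QTcF threshold is min(515, max(500, R + 60)): 500 ms for R of 440 or below, 510 ms at 450 and 515 ms at 455 or above. But these figures compare hypothetical values of R. They do not compare two ECGs that the schedule gives the same patient, and the documents give no frequency for such values. No threshold shift is claimed.

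**The dosing sentence.** Section 4.3.2 says should, foresees recording of modifications, and can be read as a general rule with Section 5.1.2.3 as a rare exception. A reader might go further the other way and infer that a site has no reduced dose it could give. That is too strong: a 245 mg administration with matching placebo exists as the Week 1 loading dose. Nothing designates it for this use, however, so the level remains unspecified. A cross-reference between the two sections would be a lighter repair, but it would leave both the unspecified dose and the weaker conditions in place. Deletion does change a management option, and it removes the explicit monitoring condition attached to that sentence.

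**Conclusion.** Both parts hold, and both are minor.

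1. If Appendix 1 has been read correctly, the ECG endpoint as worded has no scheduled reference value. Whatever the table shows, the QTcF baseline in Sections 4.5.7 and 5.1.2.3 is undefined. The effect is small, because the screening ECG is the evident reference and ECGs are only summarized descriptively.
2. Section 5.1.2.3 permits resumption at an unspecified lower dose, against the general rule in 4.3.2 and on weaker conditions than 4.3.2.1. It is confined to rare cases.

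The primary analysis, power and alpha are unaffected. Confidence is medium, mainly because of the state of the table; the Appendix 1 ECG row should be checked in the PDF.

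**What to change.** One protocol amendment, wording only, with no added visit or procedure.

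1. In the synopsis and Section 2.2, replace the randomization visit with baseline as the reference, and state that *baseline is the last value before the first dose of study drug*. Apply the same definition in Sections 4.5.7 and 5.1.2.3. As Appendix 1 reads, this gives the screening value for ECG and HbA1c, and the Day 1 pre-dose value for vital signs, hematology and chemistry. If a Day 1 ECG proves to be scheduled, the same wording selects it. Cost: the ECG reference may be up to 35 days old at first dose.
2. In Section 5.1.2.3, delete the sentence allowing resumption at a lower dose, so that discontinuation stands after a QT stopping event. Move the closing remark on clinical judgment to the end of the preceding management paragraph. Leave the exception for a clear alternative cause and the route in Section 4.3.2.1 unchanged, and add no text on resumption at full dose. Cost: a reduced dose is no longer available in a rare case.

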2.3 PHARMACOKINETIC OBJECTIVES

The pharmacokinetic (PK) objective for this study is to characterize the MSTT1041A PK profile on the basis of the following endpoint:

- Serum concentration of MSTT1041A at specified timepoints

The exploratory PK objective is as follows:

- To evaluate potential relationships between drug exposure and MSTT1041A efficacy, safety, and biomarker endpoints

2.4 IMMUNOGENICITY OBJECTIVE

The immunogenicity objective for this study is to evaluate the immune response to MSTT1041A on the basis of the following endpoints:

- Incidence of treatment-emergent anti-drug antibodies (ADAs) during the study
- Potential impact of ADA status on efficacy, safety, and PK endpoints

2.5 BIOMARKER OBJECTIVE

The exploratory biomarker objective for this study is to identify biomarkers that may provide evidence of MSTT1041A activity, or may increase the knowledge and understanding of disease biology, on the basis of the following endpoints:

- Relative change from randomization (Day 1) visit in biomarker levels in blood (see Section 4.5.6) at Weeks 1, 4, 8, 16, and 24

3. STUDY DESIGN

3.1 DESCRIPTION OF THE STUDY

This is a Phase II, randomized, double-blind, placebo-controlled multicenter study to assess the efficacy and safety of MSTT1041A in patients with moderate to severe AD. The study will consist of a screening period (Day -35 to -1), 16-week double-blind treatment period, and an 8-week follow-up period.

After providing informed consent, patients will be assessed for study eligibility during screening and at the randomization (Day 1) visit. Screening will be up to 35 days. During the screening period, patients must demonstrate EASI score ≥ 16 , IGA score ≥ 3 , pruritus NRS score for maximum itch intensity ≥ 3 , and have a history of inadequate response to treatment with topical medications. Furthermore, patients will be required to apply moisturizers (emollients) at least twice daily and to refrain from TCS or TCI use for at least the 7 consecutive days immediately before randomization and throughout the study. However, to allow adequate assessment of skin dryness, moisturizers should not be applied on the area(s) of non-lesional skin designated for such assessments for at least 8 hours before each office visit (see Sections 4.1.1 and 4.1.2 for details). Patients who fail to meet eligibility criteria during screening will be permitted to re-screen once, unless the reason for the screen failure is because of not meeting any of the following:

- EASI score ≥ 16 at screening and the randomization visit
- IGA score ≥ 3 (on the 0 to 4 IGA scale, in which 3 is moderate and 4 is severe) at screening and the randomization visit
- $\geq 10\%$ BSA of AD involvement at screening and the randomization visit
- Baseline pruritus NRS score for maximum itch intensity ≥ 3 at screening and the randomization visit

Patients who fail to meet eligibility requirements and are eligible to be re-screened are required to repeat assessments as follows:

- If ≤ 35 days after Informed Consent Form completion, repeat only the assessments that triggered screen failure.
- If > 35 days after Informed Consent Form completion, repeat the consent process and all screening assessments except tuberculosis (TB) screening and hepatitis serologies. TB screening and hepatitis serologies should be repeated if re-screening occurs > 3 months after initial Informed Consent Form completion.

[figure not shown]
At Day 1, patients will undergo further assessments to determine eligibility for randomization to the double-blind treatment period.

Approximately 90 patients will be randomized in a 1:1 ratio to receive MSTT1041A 490 mg SC or placebo SC every 4 weeks (Q4W). Randomization will be stratified by baseline disease severity IGA score (IGA=3 vs. IGA=4) and region. Patients will be given a loading dose of 245 mg SC MSTT1041A or placebo at the Week 1 visit to reduce the time required to achieve steady-state exposure of MSTT1041A (see Section 4.3.2.1 for details).

During the double-blind treatment and follow-up period, laboratory tests and clinical assessments will be performed at the site (office visits). Additionally, telephone visits will be conducted to assess changes in health status, concomitant medications, and sleep and pruritus NRS score.

[Figure 1](#) presents an overview of the study design. A schedule of activities is provided in [Appendix 1](#).

Figure 1 Study Schema

D=day; Q4W=every 4 week; Wk=week.

^a Additional loading dose on Week 1 of 245 mg MSTT1041A (or placebo) SC.

3.1.1 Internal Monitoring Committee

An Internal Monitoring Committee (IMC) will monitor data on safety and study conduct on an ongoing basis. Members of the IMC will be unblinded and will include representatives from Clinical Science and Drug Safety who are not directly involved in the study and representatives from Biostatistics and Statistical Programming and Analysis. Further details regarding roles and responsibilities will be outlined in the IMC Charter.

The IMC will review cumulative data at regular intervals of approximately every 3 months from the time of randomization of the first patient. Ad hoc meetings may be held at the request of the IMC or Sponsor at any time to address potential safety concerns. The data to be reviewed will include demographics, concomitant medications, study drug administration, adverse events, serious adverse events, adverse events of special interest, ECGs, and relevant laboratory data.

At the time of each review, the IMC will make one of the following recommendations: the trial continues as planned, the trial is stopped for safety reasons, the protocol is amended, additional analyses need to be performed, or enrollment will be held pending further safety evaluations. Decisions will be made in consideration of the totality of the available data. Final decisions will rest with the Sponsor's study team.

Any outcomes of these reviews that affect study conduct will be communicated in a timely manner to the investigators for notification of their respective Institutional Review Board (IRB) or Ethics Committee (EC).

